Protocol for Comparative Efficacy of Self-directed & Therapist-assisted Telehealth Parent
Training Intervention for Children With ASD

NCT02721381

Based on last approval by MSU IRB on 4/6/2020

Risk to Human Subjects

a. Human Subjects Involvement, Characteristics, and Design

A total sample of 90 children with ASD between the ages 18-96 months and their primary caregivers will be recruited for this study. This sample size was determined to be adequate for maintaining adequate power for the proposed statistical analyses, while allowing for some attrition.

Inclusion Criteria for Families: To be eligible for participation, 1) the child must receive a DSM-V-informed clinical diagnosis of Autism Spectrum Disorder, based on the *Autism Diagnostic Observation Schedule* (ADOS). The diagnosis may be provisional for children under age 3 (typically listed as "at risk for ASD"). Children with this classification will be included as well. (2) The child must fall between the ages of 18 - 96 months at enrollment into the study, which will allow for data collection during the period of early intervention and early childhood special education programming. (3) The parent must understand spoken English as the training materials are presented in English.

Exclusion Criteria for Families: (1) Children with ASD who have a history of significant brain injury or known neurological condition in addition to a diagnosis of ASD, significant sensory impairment or major medical problems. These children and their families may require very specific adaptations to the treatment and thus the results will not be representative of children with ASD. This will be determined through review of medical records, diagnostic reports and parent interview. Criteria and data sources for identifying participants are outlined below.

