Assignment to Study Group: Participating children and their primary caregivers will be assigned to one of three groups. Participants will be stratified by age (18-35 months; >36 months) and developmental quotient (DQ<55; DQ ≥55) at project enrollment, prior to being randomized. After stratification, participants will be randomly assigned to the one of the three groups using random permuted blocks of 6. This approach has been shown to yield groups that are closely balanced with regard to size and relevant pre-treatment characteristics. All pre-treatment assessments will be collected prior to randomization to prevent bias during testing based on knowledge of future group placement.

b. Sources of Materials

The sources of data for this study will include: (1) direct assessment of child functioning using standardized assessments; (2) completion of standardized questionnaires by parents; (3) written survey completion by parents; and (4) videotaped coding of treatment processes. All data will be used exclusively for research purposes. All surveys and interviews will use codes rather than subject names. Only the PI and primary research team members will have access to subject identities. Procedures to minimize risk of loss of confidentiality are presented below.

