Child Measures: Child diagnostic testing will be conducted at pre-treatment. We will also examine specific child characteristics (cognitive ability level, language level, autism severity) that are predicted to be related to the impact of the parent-implemented interventions. We will administer the Autism Diagnostic Observation Scale, 2nd Edition (ADOS-2) to the child at pre-treatment. The ADOS-2 is a standardized protocol for observation of social and communicative behavior associated with a diagnosis of ASD that has been shown to have high reliability and discriminant validity. Recent longitudinal studies have demonstrated that diagnostic stability for children under age 3 is best when using DSM-IV based clinical judgment in conjunction with results from standardized diagnostic instruments, such as the ADOS. As in previous studies, this is the approach that will be used in the present study in order to determine a specific DSM-V diagnosis for each child. The PI has established research reliability on the ADOS. She will train the clinical research staff on these methods (as needed) and supervise all assessments. Child cognitive ability will be assessed using the Mullen Scales of Early Learning at T1. Child intentional communication with the parent will be scored from a parent-child interaction in the home at pre-treatment and post-treatment using weighted frequency of intentional communication. Language outcomes will be assessed at pre-treatment and follow-up using the

Mullen Scales of Early Learning, a parent report measure (the MacArthur-Bates Communicative Development Inventory) and the Vineland Adaptive Behavior Scales.

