Overall Approach. The current study will use the Intention-to-Treat model (ITT) in the analysis of the primary aims. The ITT approach requires that all participants who are randomly assigned be compared on outcomes regardless of their adherence to treatment, reasons for withdrawal, or missing responses. Accordingly, we will include all participants in data analysis, follow up participants who withdraw from treatment, and impute missing data, as described below.

Missing Data. We will use the Expectation Maximization (EM) algorithm in SPSS to impute missing data for analyses that require complete data (e.g., Process Macro).

Preliminary analyses. To determine the comparability of groups on non-treatment variables after randomization, group differences will be examined for all T1 pre-treatment and descriptive variables. If significant group differences are detected for a given variable, and the variable of interest, then the variable will be used as a covariate in subsequent analyses as appropriate.

We will also examine age and DQ effects and identify whether treatment effects are moderated by either.

Aim 1: To examine the comparative efficacy of self-directed and therapist-assisted *ImPACT Online* on parent outcomes at post-treatment and the 3-month follow-up. To test our primary hypotheses for Aim 1, we will use multilevel modeling with restricted maximum likelihood estimation to examine the effect of group assignment on our primary and secondary parent outcomes. Time point (pre-treatment, post-treatment, follow-up) will be coded as a categorical variable. Change over time across groups will be estimated with the main effect of time, and between-group differences in change in outcomes will be estimated with the group by time interaction.

Aim 2: To examine the comparative efficacy of self-directed and therapist-assisted *ImPACT Online* on child outcomes at the 3-month follow-up. Three measures of verbal language will be collected at pre-treatment and follow-up. If child language measures are sufficiently correlated with each other ($r > .50$), we will create an equally weighted composite variable by z-scoring and summing the language measures. ANCOVA will be used to test for mean differences between the three conditions at follow-up. Pretest values will be included as covariates.

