Aim 3: To examine whether pre-treatment parenting stress moderates the effects of *ImPACT Online* on parent fidelity and parent self-efficacy at post-treatment. Pre-treatment parenting stress will be included in the MLM models as a covariate. The pre-treatment parenting stress by time interaction will be used to determine whether pre-treatment parenting stress moderates change over time, irrespective of treatment group. The three-way interaction of pre-treatment parenting stress, group, and time will be used to examine whether the relationship between group assignment and change over time (i.e., group slopes) varied by pre-treatment parenting stress. A significant interaction will be followed up by simple slopes analyses.

Aim 4: To examine whether gains in parent fidelity (or parent self-efficacy) and child intentional communication at post-treatment mediate the effects of the *ImPACT Online* on child verbal language at the 3-month follow-up. We will conduct two serial mediation analyses using the PROCESS macro in SPSS to examine whether gains in parent fidelity (Mediator 1) and child intentional communication (Mediator 2) at post-treatment mediate the effect of *ImPACT Online* in child outcomes at follow-up. A second serial mediation analysis will be conducted to examine whether gains in parent self-efficacy (Mediator 1) and child intentional communication (Mediator 2) at post-treatment mediate the effect of *ImPACT Online* in child outcomes at follow-up.

Aim 5 (exploratory): To identify predictors of parent adherence to *ImPACT Online* for the two treatment groups. This exploratory aim will be addressed using a multiple regression approach in which level of therapist support (self-directed versus therapist assisted) and three individual-level factors (computer and internet fluency, expectancies of treatment, and treatment acceptability) serve as primary predictors of parent adherence. We will also examine sociodemographic variables as predictors as well.

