Power Analysis. A series of power analyses were conducted using Borm, Fransen, & Lemmens⁸⁹ method for estimating sample size for analyses including a covariate. This approach takes into account the degree of association between the covariate and the outcome (r) by adjusting the required sample size required for an analysis without a covariate by $1 - r^2$ and then adding one extra participant per group. In our case, the covariate is the outcome variable as assessed at the pre-test. Analyses predicting parent fidelity (i.e., Aims 1 & 2) assumed a T1 to T2 correlation in fidelity of $r = .35$, and for self-efficacy, the T1 to T2 correlation was assumed to be $r = .75$. Across the aims involving parent fidelity we found that a sample size of 90 participants would provide 80% power to detect moderate to large effects of treatment condition (e.g., Cohen's $f = .32$). For parent self-efficacy a sample of 90 would provide 90%

power to detect moderately sized treatment effects (e.g., $f = .25$). For the child language variables we assumed a correlation between pretest and follow-up of approximately $r = .65$ for each of the three measures. Analyses predicting child language variables at follow-up controlling for pretest language scores (i.e., Aims 2 & 4) indicated that a sample size of 90 participants will have approximately 90% power to detect a moderate effect size ($f = .25$) for treatment condition.

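### Aim 4 fixes no covariates beyond an implied pretest language score, and the plan's imbalance screen cannot detect confounding of the mediator-to-mediator and mediator-to-language paths

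*Combined protocol and SAP*

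**What the plan says.** The Statistical Analysis Plan, Aim 4, sets out two serial mediation models in the PROCESS macro. The first examines whether "gains in parent fidelity (Mediator 1) and child intentional communication (Mediator 2) at post-treatment mediate the effect" of the intervention on child outcomes at follow-up. The second puts parent self-efficacy in place of fidelity. Neither lists covariates.

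Three other places bear on the question.

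- **Power Analysis.** It describes the follow-up language analyses as "controlling for pretest language scores (i.e., Aims 2 & 4". This is the only covariate the plan ties to Aim 4.
- **Preliminary analyses.** "If significant group differences are detected for a given variable", that variable becomes a covariate in later analyses where appropriate. A further clause about the variable of interest is hard to parse. A separate sentence says that age and DQ effects, and moderation by either, will be examined. It does not place age or DQ in the Aim 4 equations and does not mention autism severity.
- **Child Measures.** The study will examine "specific child characteristics (cognitive ability level, language level, autism severity) that are predicted to be related to the impact of the parent-implemented interventions".

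Under Assignment to Study Group, "Participants will be stratified by age (18-35 months; >36 months) and developmental quotient (DQ<55; DQ ≥55) at project enrollment". Autism severity is not a stratification factor. The documents state no no-confounding assumption for Aim 4 and no sensitivity analysis for mediation.

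**The concern.** Randomisation protects the effect of arm on each mediator and on language. It does not protect the path from Mediator 1 to Mediator 2, or the paths from the mediators to language, because fidelity, self-efficacy and communication gains are not assigned. A child who is older, has a higher DQ or has milder autism may both gain more intentional communication and have better language three months later. A model without that characteristic credits the shared cause to the mediator.

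A screen on arm imbalance asks a different question. It looks for chance differences between arms, whereas this bias arises within arms and is present when the arms are identical. Stratifying on age and DQ makes those two variables still less likely to pass. At stake is the mechanism claim: Aim 4 could attribute to the programme's causal chain something that was partly baseline child ability.

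**Working it through.** **The plan's own figure.** The only number tied to Aim 4 is about 90% power for treatment condition at f = .25, r = .65, N = 90. With the plan's covariate adjustment, the equivalent unadjusted N is (90 − 3)/(1 − .65²) = 87/.5775 = 150.6. A three-group F test at two-sided α = .05 (assumed; the plan states no α) then has 78% power. The 90% does not reproduce, but that is a separate matter. The figure is not power for an indirect effect, and nothing below depends on it.

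**Inputs.** From the documents: N = 90, three groups, pretest-to-follow-up language correlation .65. Assumed: 30 per arm, no dropout (no rate is given), α = .05 two-sided, and all associations and arm effects below.

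**Step 1: what the screen does.** A randomised baseline variable shows a significant arm difference about 5% of the time, however strongly it confounds (4.8–5.8% simulated without stratification). The chance that at least one of three independent variables passes is 1 − .95³ = 14.3%.

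**Step 2: the Mediator 2 to language coefficient.** Let a baseline characteristic have association g with Mediator 2 and with language, each after pretest language. The true path is zero. The spurious partial correlation is about g², and with about 85 residual degrees of freedom the noncentrality is g²√85/√(1 − g⁴).

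| g | g² | Noncentrality | Rejection by formula | Simulated, characteristic omitted | Simulated, characteristic included |
|---|---|---|---|---|---|
| .2 | .04 | 0.37 | 6.5% | about 6% | about 5% |
| .3 | .09 | 0.83 | 13% | about 14% | about 5% |
| .4 | .16 | 1.49 | 31.5% | about 30% | about 5–6% |

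The simulated values adjust for arm, Mediator 1 and pretest language (4,000 trials each). Applying the imbalance screen instead gives 5.9%, 12.9% and 30.8%, so the rule barely helps.

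**Step 3: indirect effects.** A false indirect effect also needs a significant arm-to-mediator link. The test here is joint significance of the component paths, standing in for the PROCESS bootstrap. Assumed arm effects are 0.5–0.8 SD on Mediator 1 and 0.3–0.5 SD on Mediator 2. The largest false-positive rates with pretest language adjusted are:

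| Path | g = .2 | g = .3 | g = .4 |
|---|---|---|---|
| Arm → Mediator 2 → language | 4% | 7% | 17% |
| Arm → Mediator 1 → Mediator 2 → language | 0.5% | 1.4% | 7% |
| Arm → Mediator 1 → language, if the characteristic also drives Mediator 1 | 6% | 12% | 23% |

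The serial maxima also come from cases where the characteristic drives Mediator 1.

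**Step 4: a second parameterisation.** Here an ability index correlates .5, .7 or .8 with pretest language. Its effects on Mediator 1, Mediator 2 and language are .3, .3, .3 (moderate) or .4, .5, .4 (stronger). Arm effects are 0.8 SD on Mediator 1 and 0.6 SD on Mediator 2. There are 2,000 trials per case. The table shows false significance of the Mediator 2 coefficient.

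| Correlation with pretest language | Confounding | Pretest language only | With imbalance screen | Ability in model |
|---|---|---|---|---|
| .5 | moderate | 11.8% | 11.8% | 4.6% |
| .7 | moderate | 8.0% | 7.9% | 4.3% |
| .8 | moderate | 6.4% | 6.2% | 5.2% |
| .5 | stronger | 37.4% | 36.0% | 5.2% |
| .7 | stronger | 23.3% | 22.3% | 5.2% |
| .8 | stronger | 14.8% | 14.3% | 4.9% |

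Across these cases, with pretest language only, the false serial path runs 0.2–10.6% (0.2–0.4% with ability included). The arm → Mediator 2 → language path runs 4–19% (3–4% with ability included).

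**The case against.** The plan is silent rather than prohibitive. A reader might infer that age, DQ and severity can enter Aim 4 only through imbalance. The documents do not support that: age and DQ effects are to be examined with no imbalance condition attached, and the screen's wording is loose. What stands is narrower: no sentence puts these variables in the Aim 4 equations, so the choice stays open after the data are seen.

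The associations are assumed. Pretest language probably carries much of DQ, since the Mullen supplies both cognitive ability and one of the three language measures. Defining the mediators as gains may remove more. This stands: at g = .2, or with moderate confounding and a correlation of .8 with pretest language, the rate is about 6% against a nominal 5%. The argument has less force for age and severity.

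A reader might also take Child Measures as proof of confounding. It predicts a relation to the interventions' impact, which reads most naturally as moderation. It makes confounding plausible but does not establish it.

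Finally, Aim 4 is a mechanism question, and the Aim 1 and Aim 2 efficacy comparisons are untouched. That is right, and it limits the weight of the point.

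**Conclusion.** The concern holds as a gap in pre-specification combined with a selection rule unsuited to mediation. With a residual association of .3 or more, omitting the characteristic raises false significance of the Mediator 2 to language coefficient from about 5% to about 14%, and to about 30% at .4. At .2 the effect is negligible.

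A reader might take those single-coefficient rates as the chance of a falsely reported mediation chain. They are not. The plan's serial hypothesis also needs arm → Mediator 1 and Mediator 1 → Mediator 2, and its false-positive rate stays at or below about 7% for associations up to .4 in Step 3. It reaches 10.6% only in the most adverse case of Step 4. The shorter indirect paths are more exposed: up to about 17% through Mediator 2 and 23% through Mediator 1 at .4. All of this rests on assumed associations and arm effects, complete data and joint-significance testing. The direction of the argument does not: balance between arms gives no assurance about these paths.

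**What to change.** Add to Aim 4 that T1 age, T1 DQ, T1 ADOS severity, pretest language and the baseline values of that model's two mediators enter the mediator and language equations of both PROCESS models, whether or not the arms differ on them. State that the imbalance screen under Preliminary analyses does not govern Aim 4.

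The cost is a sentence or two and a few residual degrees of freedom: three for age, DQ and severity and two for the baseline mediator values, so about 85 falls to about 80. The variables precede randomisation, so adjustment introduces no post-treatment bias, and all are already collected. The change does not deal with unmeasured confounders. The report should say so, and a sensitivity analysis for unmeasured mediator-outcome confounding would be a useful addition.

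### Aim 4 neither defines the mediator gains nor enters the mediators' pre-treatment scores; if raw differences are used, precision is lost and the later mediation paths can be biased

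*Combined protocol and SAP*

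**What the plan says.** Under Aim 4 the plan states: "We will conduct two serial mediation analyses using the PROCESS macro in SPSS". The mediators in the first model are "gains in parent fidelity (Mediator 1) and child intentional communication (Mediator 2) at post-treatment"; in the second they are "gains in parent self-efficacy (Mediator 1) and child intentional communication (Mediator 2) at post-treatment". The outcome is child verbal language at the 3-month follow-up. Aim 4 gives no formula for a gain and no covariate list.

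Three other places bear on the point:

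- **Power Analysis.** The calculations rest on covariate adjustment: "In our case, the covariate is the outcome variable as assessed at the pre-test". The assumed pre-to-post correlations are .35 for fidelity and .75 for self-efficacy. Aim 4 is named only for language at follow-up, controlling for pretest language.
- **Preliminary analyses.** A pre-treatment variable becomes a covariate only if the groups differ significantly on it. That does not ensure that the mediators' baselines enter.
- **Aim 2.** Here the plan says outright that pretest values are covariates. Aim 4 has no matching sentence for its mediators.

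The second mediator is scored as "weighted frequency of intentional communication" at pre- and post-treatment (Child Measures). No correlation is assumed for it.

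**The concern.** A raw difference carries the noise of two measurements and is negatively correlated with the starting value, so families who start low tend to look like gainers. Randomization protects the comparison of gains between groups. It does not protect the regression of one mediator on another, or of language on a mediator, because neither mediator is randomized. If the baselines of fidelity, communication and language are related, part of that relation passes into the mediator paths. Two analysts could both follow the text, one with raw differences and one with baseline-adjusted scores, and reach different conclusions about mechanism.

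**Working it through.** **Inputs.** From the Power Analysis: N = 90, r = .35 and f = .32 for fidelity, r = .75 and f = .25 for self-efficacy. From Assignment to Study Group: three groups. Assumed, because not stated: alpha .05, a 2-df F test, 30 per group, and equal pre and post variances (set to 1).

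**1. The plan's own figure.** The plan says that "a sample size of 90 participants would provide 80% power" for fidelity. Without a covariate, 80% power at f = .32 needs 99 participants. The plan's adjustment gives 99 × (1 − .35²) + 3 = 89.9, so 90. The figure reproduces, and it presumes adjustment for the pre-test.

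**2. Residual variance.** A raw gain has variance 2(1 − r). The post score adjusted for the pre score has 1 − r². The ratio is 2/(1 + r).

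| Mediator | Raw gain | Adjusted | Variance ratio | SD ratio |
|---|---|---|---|---|
| Fidelity, r = .35 | 1.300 | .8775 | 1.48 | 1.22 |
| Self-efficacy, r = .75 | .500 | .4375 | 1.14 | 1.07 |

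For fidelity the correlation of gain with pre score is −(1 − .35)/√1.30 = −.57. The 48% depends on equal variances: at assumed post/pre SD ratios of 0.75, 1.25 and 1.5 it becomes 110%, 23% and 11%. Nothing can be computed for intentional communication without a correlation.

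**3. Treatment to first mediator.** The noncentrality is N f² divided by the residual variance.

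- Fidelity: 90 × .1024/.8775 = 10.50, power 82%; with raw gains 90 × .1024/1.30 = 7.09, power 65%.
- Self-efficacy: 90 × .0625/.4375 = 12.86, power 89%; with raw gains 90 × .0625/.50 = 11.25, power 85%.

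The estimate itself is unbiased. In simulation with a true effect of .60, both methods return .60.

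**4. Mediator to outcome.** Let the outcome depend on the post-treatment mediator with slope b and on its baseline with slope g. Regressed on the raw gain and group, the slope has expectation b − (b + g)/2 = (b − g)/2. With b = .30 (assumed) this is .15 if g = 0, zero if g = .30, and .30 if g = −.30. Simulation agrees. Adding the pre-treatment mediator returns .30 each time. The raw gain is right only when g = −b, that is, when the difference itself is the cause.

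**5. Mediator to mediator, no true effect.** Assume communication stability .5, a common correlation c among the three baselines, and pretest language in the model. The residual covariance of the two gains is (1 − .35)(1 − .5)(c − c²). The residual variances are .4225(1 − c²) + .8775 and .25(1 − c²) + .75.

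- c = .3: covariance .0683, variances 1.262 and .978, partial correlation .061, rejection rate about 9%.
- c = .5: covariance .0813, variances 1.194 and .938, partial correlation .077, rejection rate about 11%.

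Simulations with 3 × 30 participants give about 8-12% for raw gains and about 5% for the adjusted model. With uncorrelated baselines both are nominal.

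**6. Serial indirect effect.** These are simulated powers for therapist-assisted against control, with both later paths .3, stabilities .5 (communication) and .65 (language), and a Monte Carlo interval. Of these inputs only .65 is in the plan.

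| What drives the chain | Adjusted | Raw gains |
|---|---|---|
| Post-treatment levels, baselines uncorrelated | 60% | 9% |
| Post-treatment levels, baseline correlations .3 to .5 | about 59% | 18-29% |
| Raw gains | 57% | 59% |

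With no true mediator-to-mediator effect, the serial test on raw gains rejects below 5% of the time (about 2-3%).

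**The case against.** The strongest reply is that the plan never says raw differences will be used. A residualised gain, or a post score with the pre score as covariate, also fits the word. That stands: unadjusted differences are the usual reading, not a stated method. The firm finding is that the definition and the covariates are missing. The figures show what follows under the usual reading.

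A reader might infer that Aim 4 is less efficient than the design claims. The documents do not support this. The Power Analysis ties the fidelity correlation to Aims 1 and 2, and for Aim 4 it claims power only for the treatment effect on language. It states no power for any mediator path or indirect effect, so 65% against 82% compares two methods and is not a broken promise.

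A reader might also infer that false mediation claims would be inflated. The excess concerns the single mediator-to-mediator path. The serial effect, which Aim 4 is about, stays at or below nominal under the same assumptions.

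Finally, the 60% against 9% contrast is an extreme case. It needs uncorrelated baselines and level-driven effects, whereas the 8-12% figure needs correlated baselines, so the two should not be cited together. If gains drive the chain, which is one way to read Aim 4's hypothesis, there is no material difference.

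**Conclusion.** The point holds in conditional form. Aim 4 leaves its mediators undefined and does not provide for their pre-treatment values. If raw differences are used:

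- Fidelity loses precision appreciably and self-efficacy slightly. The 48% is a variance ratio for fidelity alone, under equal pre and post variances. It is not an SD figure and does not extend to the other mediators.
- The treatment-to-mediator path is not biased.
- The later paths can be biased by an amount the documents cannot fix: in the worked example, from none to the whole of the effect.
- Power for the serial effect can fall substantially if post-treatment levels drive the chain, and is about unchanged if raw gains do.

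The main consequence is a real chain being missed, or a single link misread. The treatment comparisons in Aims 1 and 2 are unaffected. The correction is nearly free and should be made.

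**What to change.** State in Aim 4 that, in both PROCESS models, each mediator is its post-treatment score. List as covariates in every equation the pre-treatment scores of fidelity (or self-efficacy in the second model), of intentional communication and of language. Enter them regardless of whether the groups differ at baseline. If the investigators do intend raw differences, the plan should say so and give the reason, with the adjusted model as a sensitivity analysis.

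All these scores are already scheduled at pre-treatment (Child Measures and Parent Measures). Relative to a model with pretest language alone, the cost is two covariates, hence two degrees of freedom per equation, and a change of wording. No new data are needed.

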Parent Measures: Parents will complete the Parenting Sense of Competence Scale at pre-treatment, post-treatment, and follow-up to assess parent self-efficacy. Using the videotapes of the parent-child interaction in the home at pre-, post-treatment, and follow-up, the research team will assess parent use of the intervention strategies. Parents will also be asked to provide demographic information and complete the Parent Expectancies for Therapy Scale, a measure of treatment expectancy, the Computer-Email-Web Fluency Scale, a measure of computer/internet fluency, at pre-treatment, and the Parenting Stress Index, a measure of parenting stress at pre-treatment. Parents will be asked to complete the Treatment Evaluation Inventory, measure of treatment acceptability, at the conclusion of treatment. Parents will complete the Additional Services Form to monitor the type and number of hours per week of all non-study treatments once per month throughout study participation.

c. Potential Risks

There are no known serious health or psychological risks related to participation in this study. Procedures to minimize risk of loss of confidentiality are presented in the following section. In addition, there are legal limits to the confidentiality of information obtained during the research study. All information obtained from participants will be held confidential unless there is serious threat of harm to a child or to self or others. These limitations will be addressed in the consent forms. Collection of data from participants will include standardized child assessment measures, standard parent questionnaires regarding their child's development and behavior, standard parent questionnaires about their well-being and satisfaction with treatment, and videotape recordings. Precautions will be applied to all collected data from these activities, which will be stored in a private, secure and confidential location at MSU. All participants will be made aware of how collected data will be handled.

Adequacy of Protection Against Risks

a. Recruitment and Informed Consent

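### Exploratory Aim 5 treats acceptability, rated only at the end of treatment, as a predictor of adherence beside randomised therapist support, and specifies no model without it

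*Combined protocol and SAP*

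**What the plan says.** The Statistical Analysis Plan labels the aim and states its purpose: "Aim 5 (exploratory): To identify predictors of parent adherence to" the online programme, in the two treatment groups. The method is a "multiple regression approach in which level of therapist support (self-directed versus therapist assisted) and three individual-level factors", and those factors are then named: "computer and internet fluency, expectancies of treatment, and treatment acceptability) serve as primary predictors of parent adherence". Sociodemographic variables are to be examined too. The plan gives no order of entry and no model that leaves acceptability out.

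The timing is in the Parent Measures paragraph. Expectancy and fluency are baseline measures: "a measure of treatment expectancy, the Computer-Email-Web Fluency Scale, a measure of computer/internet fluency, at pre-treatment". Acceptability is not: "Parents will be asked to complete the Treatment Evaluation Inventory, measure of treatment acceptability, at the conclusion of treatment". No earlier acceptability rating appears anywhere in the document.

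Therapist support is the one randomised predictor in the model. Under Assignment to Study Group, "participants will be randomly assigned to the one of the three groups using random permuted blocks of 6".

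**The concern.** Two problems follow from the timing.

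1. **Direction.** If adherence builds up during treatment, a rating made when treatment ends cannot predict it prospectively. Parents who used the programme more may rate it more highly because they used it. The plan would list that rating beside two baseline measures with nothing to mark the difference, and could report a consequence of adherence as one of its predictors.

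2. **Adjustment after randomisation.** Support was randomised, so a model with support and baseline variables estimates its total effect on adherence. Acceptability can itself respond to support. Conditioning on it changes what the support coefficient means whenever acceptability differs between arms and is related to adherence given support. If either condition fails, nothing shifts.

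At stake is the reading of Aim 5: whether acceptability is called a predictor, and whether therapist support is picked out as one. The second can depend on whether acceptability is in the model, and the plan specifies no model that would show this.

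**Working it through.** The documents state no effect size or power for Aim 5, so there is no planned figure to reproduce. The timing mismatch comes from the text. The sizes below illustrate it under stated assumptions.

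**Timing of the predictors**

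| Aim 5 predictor | When fixed or measured |
|---|---|
| Therapist support | Randomisation, after the pre-treatment assessments |
| Computer and internet fluency | Pre-treatment |
| Expectancy | Pre-treatment |
| Acceptability | Conclusion of treatment only |

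**Inputs**
- From the documents: 90 families in three groups. Equal allocation is assumed (blocks of 6 fit it, but the ratio is not stated), giving 30 per arm and 60 in the two treatment groups.
- Assumed: total support effect dT = 0.5 SD; within-arm variances of 1 for adherence A and acceptability Q; within-arm correlation rho; direct effect t of support on Q; two-sided 5% tests.
- Attrition: the design section speaks of "maintaining adequate power for the proposed statistical analyses, while allowing for some attrition" without a rate. Losses of 10% and 20% are assumed, giving 54 and 48 families.

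**Formula.** Let Delta be the arm difference in Q. With unit within-arm variances, the slope of A on Q given support is rho, so

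adjusted support coefficient = dT − rho × Delta.

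**Case 1: adherence drives acceptability.** Q = rho·A + t·T + error, where T is support (0/1), so Delta = rho × 0.5 + t.

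| rho | t | Delta | Adjusted coefficient | % of total |
|---|---|---|---|---|
| 0 | any | t | .500 | 100% |
| .3 | 0 | .15 | .5 − .045 = .455 | 91% |
| .5 | 0 | .25 | .5 − .125 = .375 | 75% |
| .3 | +0.5 | .65 | .5 − .195 = .305 | 61% |
| .5 | +0.5 | .75 | .5 − .375 = .125 | 25% |
| .3 | −0.5 | −.35 | .5 + .105 = .605 | 121% |
| .5 | −0.5 | −.25 | .5 + .125 = .625 | 125% |

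Simulation with n = 2,000,000 gives .457, .375, .305, .126, .604 and .625 for the last six rows. With t = 0 the ratio is 1 − rho², whatever the total effect.

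**Case 2: acceptability drives adherence**, with Delta = 0.5. The coefficient is .5 − .3 × .5 = .35 (70%) or .5 − .5 × .5 = .25 (50%). This is a direct effect of support, not its total effect.

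**Against sampling error.** The standard error of the arm contrast is sqrt(2/30) = .258 with 60 families and sqrt(2/24) = .289 with 48. The case 1 shifts of .045 to .375 are 0.17 to 1.45 standard errors with 60 families, and 0.16 to 1.30 with 48.

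**Chance that support is significant** (case 1; 20,000 simulated trials per cell; two independent baseline covariates in every model)

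| Model | 60 families | 48 families |
|---|---|---|
| Without acceptability | 46% | 38% |
| With it, t = 0, rho .3 / .5 | 43% / 36% | 34% / 29% |
| With it, t = +0.5, rho .3 / .5 | 20% / 8% | 17% / 7% |
| With it, t = −0.5, rho .3 / .5 | 64% / 75% | 54% / 65% |

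**Chance that acceptability is flagged when it only follows adherence** (t = 0, rho .3 / .5): 63% / 98% with 60 families, 58% / 97% with 54, 53% / 95% with 48. The Fisher z approximation, Φ(atanh(rho) × sqrt(n − 6) − 1.96), gives 62% / 98%, 57% / 97% and 52% / 95%. At rho = 0 the rate is about 5%. These figures are power to detect a real association, not a type I error; the association simply runs from adherence to the rating.

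**A different assumed effect.** With a total effect of 0.8 SD and 60 families (4,000 trials per setting, no covariates), the model without acceptability recovers about 0.80. Adding acceptability that follows adherence gives 0.72 (slope .3) or 0.59 (slope .5). If support also raises acceptability directly, the coefficient falls to 0.58 (slope .3, direct effect 0.5) or 0.45 (slope .5, direct effect 0.3). With no true effect of support, the slope .3, direct effect 0.5 setting gives −0.15.

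**The case against.** The strongest reply is that Aim 5 promises little. It is exploratory, it sets out to find predictors, and it never says that the total effect of support is wanted. The plan ties intention-to-treat to the primary aims. In a regression of this kind, a predictor may mean no more than a regressor, and the acceptability coefficient is a valid adjusted association. The adherence measure and its window are undefined, so the time order is inferred. A regression approach does not rule out staged entry. Every effect size above is assumed. Without a direct effect of support on acceptability, the shifts are only 0.17 or 0.48 standard errors with 60 families. The smaller sample sizes are also uncertain, because the plan intends to follow up families who withdraw and to impute where complete data are needed, without saying whether that covers Aim 5.

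Much of this stands. It fixes the priority as low and means that neither the size nor the direction of the shift can be known now. The simple arm contrast could also still be computed from the same data.

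It does not remove the point. Exploratory status does not make an end-of-treatment rating comparable with a baseline measure. Staged entry is possible but not specified. A different adherence window would weaken the direction argument, but acceptability would still be a post-randomisation variable in the model that contains support.

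**Conclusion.** The concern holds, at low priority. As written, the plan adjusts its one randomised predictor of adherence for a rating made after randomisation, and lists that rating as a predictor although it may be a result of adherence.

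Under the assumed values, the adjusted support coefficient is anywhere from 25% to 125% of the total effect. It is 91% or 75% in the plainest case, where acceptability only follows adherence. There is no shift if acceptability does not differ between arms or is unrelated to adherence given support.

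The reading of acceptability as a consequence rests on adherence accruing during treatment, which the documents do not state. The Power Analysis section does not name Aim 5, no decision rule depends on it, and Aims 1 to 4 are unaffected.

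**What to change.** Make the main Aim 5 model a regression of adherence on therapist support and pre-treatment variables only (computer fluency, expectancy, sociodemographics), and take the support estimate from it. Then either add acceptability in a second step labelled as such, or report it as a post-treatment correlate of adherence. Do not read the support coefficient from that second step as the effect of support. State the adherence measure and its time window in the same paragraph, since the interpretation depends on them.

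The cost is a change of SAP wording, with no data beyond the measures already planned. The downside is that one planned predictor moves out of the main exploratory model into a second step or a descriptive analysis.
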